**Group and 1:1 Facilitation:**

- SSPs in the DI arm will meet as a group to actively discuss problem solving for implementation barriers encountered.
  - At least 1 consistent SSP from each site will be required to attend. Sites will be encouraged to send the most knowledgeable and involved individuals in the implementation to the meetings.
  - Group facilitation should occur quarterly, as needed.
- SSPs in the DI arm will be offered one-on-one facilitation calls to help problem solving for individual implementation barriers.
  - At least 1 consistent SSP will participate in the one-on-one calls.
  - One-on-one facilitation calls will be up to monthly as needed except for the months when group facilitation occurs.

**FRAME-IS:**

- SSPs at each site will complete the FRAME-IS questionnaire each month, which will be sent via email. Additional details on the FRAME-IS are provided in the SRM.

The full SoA can be found in [ANNEX 1](#) and [ANNEX 2](#).

**4.1.4. Primary Endpoint**

The primary endpoint is Feasibility of Intervention Measure score assessed from SSP Month 13. The secondary implementation endpoints include the feasibility in PSPs, feasibility and acceptability of specific implementation components, reach, fidelity, and utility. Additional secondary measures will assess awareness, uptake, adherence and retention of APRETUDE, adaptations to existing toolkits, and the process of acquiring Cabotegravir. Quantitative and qualitative data as well as facilitation calls and FRAME-IS output will be triangulated to inform final study results.

**4.1.5. Telehealth Strategy**

Telehealth is a unique strategy within the dynamic implementation arm requiring its own standard operating procedures. Telehealth delivery of APRETUDE is new and is likely to be complex with no similar benchmarks with which to compare. It is important to understand and resolve the known and unknown challenges that may accompany telehealth delivery of APRETUDE before attempting to scale as unresolved challenges can lead to significant opportunity costs. For these reasons, the telehealth strategy will be approached from a developmental evaluation lens, which is an approach that supports continuous adaptation in complex environments, emphasizing iterative, real-time data collection and regular reflection to support adaptation [Fagen, 2011]. Developmental evaluation creates a road map to ensure the right people are reflecting on the right data at the right time to inform changes and that careful, ongoing documentation is occurring in the implementation process.

The approach may provide the foundation for producing the essential information, such as development and design, and optimal strategies for the possible scale-up of telehealth delivery of APRETUDE. The telehealth strategy may be a simulated digital environment or a hybrid system of integrating telehealth components/modules into existing clinic telehealth systems. This will be done in a sub-group of clinics in the study.

Certain functions within the telehealth platform will be made available to potential patients of the PrEP provider as part of routine care and is independent of study participation. Some patients, however, may subsequently become study participants if eligible. Potential patients may take a web-based/online questionnaire, such as the Sexual Health Assessment Tool, that is being implemented as routine care for all men within a clinic. Any questionnaire data collection will only be done following the patient's agreement to consent to data sharing and privacy terms within the platform. Data collected from potential patients will be key coded and reviewed by the provider in order to provide appropriate PrEP care to their patient. Data collected for study purposes (i.e., shared with CRO) will be de-identified in aggregate form only at the site level data is not connected to any individual. Once a patient is linked to a PrEP provider for consideration and provision (including prescribing and administration of APRETUDE injections), then the site staff may consider initiating a discussion around involvement in the study and initiation of study consent discussions. The telehealth strategy may include, but is not limited to:

- Patient web-based/online PrEP questionnaires (e.g. Sexual Health assessment, this does not include the questionnaires noted in the SoA).
- Online appointment scheduling for providers.
- Initial patient-provider interaction through telehealth.
- Provider ability to provide an HIV test or schedule a lab draw (at local lab) during the initial telehealth visit.
- Electronic submission of the HIV test result or result of the lab draw to the PrEP provider.
- Electronic submission of optional oral lead-in prescription from provider (if needed)
- Electronic scheduling of first IM dose for patient from a choice of sites. Potential locations for injection visits at clinic (scheduled or drop-in), or patient home (if allowed).
- Patient benefits verification process (e.g., insurance)
- Home nursing option for home administration (if feasible).
- PSP injection visit scheduling at chosen location.
- Follow-up visits occur with provider via telehealth.

The digital environment developed for this study could be utilized to support future telehealth strategies and designs. Implementation assessments (e.g., facilitation calls, FRAME-IS) may also document the telehealth processes to help inform future scale up. Detail information on the telehealth strategy is given in the SRM.

## 4.2. Scientific Rationale for Study Design and Research Methods

The HPTN 083 and HPTN 084 studies demonstrated that the efficacy of APRETUDE was statistically superior to daily oral FTC/TDF for PrEP at preventing HIV acquisition in cisgender men who have sex with men and transgender women as well as cisgender women, respectively. Yet, clinical efficacy of a product often does not translate to real-world effectiveness, including awareness, knowledge, demand, acceptability and use. Research shows that just because an effective treatment exists, translation into routine care is slow and often never occurs [Bauer, 2020]. For long acting injectables for HIV prevention, however, early acceptability research has shown preference for an injectable prevention method over other methods by end-users [Philbin, 2021; Tolley, 2020]. However, as the first injectable HIV prevention modality, APRETUDE will require changes to the current routine of prescribing oral PrEP therapy, including but not limited to workflow, staffing needs, delivery platform considerations, and training needs [Pleuhs, 2020]. Therefore, implementation research will be used to identify and understand the strategies that will enhance the delivery and/or integration of APRETUDE into existing and new PrEP delivery systems and programs is critical to its access and use.

Implementation research focuses on systematic uptake of research findings into routine practice in order to improve health services. The study will be guided by a set of evidence-based implementation frameworks to ensure the robustness of the research. Implementation outcomes will be identified and measured at the service and patient level in order to determine how effectively and efficiently APRETUDE is being integrated and delivered within the identified clinics. The study will identify the barriers and facilitators to effective implementation while allowing for the tailoring and adapting of strategies to fit the needs of each clinical setting. As a result, this proposal is guided by frameworks that are appropriate to the proposed stage of implementation research, including both a process and determinants framework and an outcomes taxonomy.

The study design utilizes unequal randomization ratio of 2:1, whereby twice as many clinics are allocated to the DI arm than the RI arm. Unequal allocation is chosen due to the unequal distribution of implementation resources between the two arms. The DI arm will receive several enhanced supports relative to the RI arm and therefore, unequal allocation is recommended [Dumville, 2006].

[figure not shown]
### 4.2.1. Implementation Frameworks

The study is guided by 3 Gold Standard Implementation Science Frameworks (covering evaluation, determinants, and process): the Proctor [Proctor, 2011] Outcomes Framework, the Consolidated Framework for Implementation Research (CFIR) [Damschroder, 2009] and the Framework for Reporting Adaptations and Modifications to Evidence-based Implementation Strategies (FRAME-IS) [Miller, 2021].

The Proctor outcomes framework will provide guidance on study design and outcomes [Proctor, 2011]. The framework distinguishes between three distinct but interrelated types of outcomes – implementation, services and client health outcomes. Improvements

in client health outcomes (e.g., remaining HIV uninfected) and service outcomes (e.g., on-time APRETUDE injections) are impacted by the implementation process and implementation outcomes. The framework will be used to guide measurement decisions for the key outcomes that will be assessed: feasibility, fidelity, acceptability, utility and reach.

**Figure 3 Proctor & CFIR Integration Application**

CFIR will be integrated with the Proctor outcomes framework to serve as the process and determinant's framework. CFIR provides a repository of standardized implementation-related constructs organized across five major domains that influence implementation and implementation effectiveness - intervention characteristics, outer setting, inner setting, characteristics of individuals involved, and the process of implementation. These constructs can be used in a range of applications and for this study, CFIR will be integral to systematically identifying and assessing barriers and facilitators to APRETUDE implementation via the implementation strategies. The framework can be used to develop data collection approaches and therefore, will be used to guide the qualitative interviews with study participants and Study Staff Participants.

Adaptations made to the toolkits, RI and DI will be captured using the FRAME-IS [Miller, 2021]. The FRAME-IS provides a systematic way of documenting and tracking modifications to implementation strategies in traditional healthcare settings, allowing for a better understanding of how the strategies influence outcomes. It is modular, capturing what is modified, the nature of the modification, and the rationale for the modifications. There are also optional modules to capture when modifications occurred, whether they were planned, who participated in the decision making and how widespread they were.

## 5. Statistical Considerations

The statistical analysis plan will be finalized prior to any interim or final database lock (DBL) and it will include a more technical and detailed description of the statistical analyses described in this section. This section is a summary of the planned statistical analyses of the most important endpoints including primary and key secondary endpoints.

Baseline analyses will be conducted when a sufficient number of SSPs and PSPs complete their baseline assessments. Interim analyses will be conducted when a sufficient number of staff study and/or patient study participant complete study assessments up to the Month 5 time point for SSPs and the Month 7(OLI)/Month 6(DTI) time point for PSPs. Additional interim analysis may be performed as required and will be detailed in the Statistical Analysis Plan (SAP). The purpose of these interim analyses will be to provide early evaluation of the implementation science primary and key secondary objectives.

Completed SSP and PSP questionnaire and interview data collected at the time of the interim data cut, will be included in the analyses. In addition, a limited number of clinical datasets from the eCRF will be included in order to describe the characteristics of the patient study participants enrolled. No formal criteria for stopping or amending the study based on interim analysis results will be made. The SAP will describe the planned analyses in greater detail.

### 5.1. Statistical Hypotheses

The primary hypothesis on the quantitative aspects of this study is that there is a difference between the dynamic implementation (DI) strategy and the routine implementation (RI) strategy in terms of staff study participants' (SSPs) mean FIM score at Month 13, i.e.,

$$H_{10} : \mu(\text{DI}) = \mu(\text{RI}) \text{ vs } H_{11} : \mu(\text{DI}) \neq \mu(\text{RI}),$$

and the secondary hypothesis is that there is a difference between the dynamic implementation (DI) strategy and the routine implementation (RI) strategy in terms of patient study participants' (PSPs) mean FIM score at Month 13, i.e.,

$$H_{20} : \mu(\text{DI}) = \mu(\text{RI}) \text{ vs } H_{21} : \mu(\text{DI}) \neq \mu(\text{RI}).$$

The two-way ANOVA will be used to test each of the above hypothesis with clinic volume as the stratification factor, where no multiplicity adjustment is planned.

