- To evaluate feasibility and acceptability of telehealth delivery for APRETUDE administration by clinical staff.
- To evaluate acceptability and utility of DI compared to RI for APRETUDE administration
- To evaluate fidelity to injection and dosing window

- To evaluate fidelity and reach of client Sexual Health Assessments for APRETUDE
- To evaluate adaptations to any implementation strategies used in clinics to include, but not limited to, modifications to toolkits, RI and DI to support APRETUDE implementation
- To evaluate switch from oral PrEP to APRETUDE
- To evaluate perceptions, barriers and facilitators with Staff Study Participants (SSPs) and Patient Study Participants (PSPs)

**Study Design:** This post-approval, Phase 4 study is designed to evaluate the impact of two implementation strategy conditions – dynamic implementation and routine implementation – on the feasibility of delivering APRETUDE in high and low volume current PrEP sites for MSM and TGM over 12 months. Approximately 18 sites will be randomized 2:1 in the Dynamic (DI) or Routine (RI) implementation arms. Randomization will occur at the level of study sites and the study will enroll the staff at the study site (who are enrolled as “Staff Study Participants”). Approximately 220 HIV negative individuals will be enrolled once CAB PrEP is prescribed to them (“Patient Study Participants”); at least 50% will be Black or Latino. Patients Study Participants will start APRETUDE using commercial product as prescribed by the PrEP provider. The study will not use a central laboratory, and all laboratory assessments will be performed according to the Centers for Disease Control and Prevention (CDC) clinical management guidelines for PrEP [[Centers for Disease Control and Prevention](#), 2021] and APRETUDE USPI using sites local laboratories [[APRETUDE](#), 2021].

Sites randomized to RI will have access to the standard CAB LA for PrEP toolkits for providers and patients to use as needed. Sites randomized to DI will receive enhanced toolkits for providers and patients, a digital health end to end implementation strategy, and implementation facilitation.

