Implementation science methodology using both quantitative and qualitative measures will be used to assess the outcomes, to determine effective implementation strategies and to identify barriers and facilitators (including solutions). The implementation outcomes will be assessed from the perspectives of SSPs and PSPs. Clinical data will be collected from PSPs to monitor safety and efficacy.

**Analysis Methods:** The primary endpoint in terms of feasibility is SSPs’ mean FIM score at Month 13 under Dynamic Implementation (DI) arm and Routine Implementation (RI) arm respectively, and the difference of SSPs’ mean FIM scores between two arms at Month 13. Descriptive statistics including 95% confidence intervals (CI) for these estimates will be displayed. A hypothesis test will be conducted to determine if the observed difference is statistically significant. To address the potential intra-cluster correlation effect due to the cluster randomization design, classical methods such as mixed effects linear regression model or Generalized Estimating Equations will be utilized. Besides the analysis on the subject level, the stratification analysis will be performed at the site level to evaluate the impact of the capacity of sites (high volume vs low volume) in responding to two implementation strategies imposed on SSPs. Exploratory analysis will be undertaken to assess the variability of responses by other

factors such as subset of implementation strategies. In addition to summary of FIM scores of SSPs at different timepoints, the change in FIM scores of each item from baseline will be analyzed at the designated timepoints. For the specific Telehealth implementation strategy on SSPs, the subgroup analysis on FIM scores including change from baseline will be conducted.

The FIM scores of PSPs will be summarized in the same way as those of SSPs. In addition, subgroup analysis on PSPs will include factors such as demographic, baseline characteristics and initiation method. To address the potential differential dropout rates of PSPs between arms, appropriate imputation methods will be undertaken to handle missing data of different type.

The analysis methods for the secondary endpoints of acceptability, utility, reach, fidelity and adaptations will be similar to that of the feasibility endpoints.

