## 4. Implementation Research Methods

### 4.1. Study Arms Overview

The two study arms are routine implementation and dynamic implementation. Clinics will be randomized to the two study arms in a 2:1 distribution, whereby about 12 clinics will be in the dynamic implementation arm and about 6 clinics will be in the routine implementation arm (Note: Number of clinics may vary depending on recruitment). Clinics receiving routine implementation will receive standard provider and patient toolkits that will be available when CAB PrEP is commercially available. Clinics receiving dynamic implementation will receive enhanced toolkits, a digital health end to end implementation strategy, and implementation facilitation. An overview of the RI and DI implementation strategies are outlined in [Table 1](#) and [Table 2](#) in terms of six dimensions as recommended by Proctor and colleagues [[Proctor](#), 2013]: actor, the action, action targets, dose, implementation outcomes addressed, and theoretical justification.

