### 5.2. Study Size

The study is designed to mainly evaluate feasibility and acceptability of some implementation strategies from the feedbacks of SSPs and PSPs using implementation science measures. The study size for SSPs and PSPs will be investigated on the basis of analysis of the standardized effect size

$$d = \frac{\mu(\text{DI}) - \mu(\text{RI})}{\sigma}$$

which is defined as the ratio of difference of mean FIM scores between two arms to the standard deviation  $\sigma$ . To accommodate various scenarios of the mean difference between

arms and the assumed standard deviation, the standardized effect size  $d$  is considered without taking into account the effect of ICC (Intra-Cluster Correlation).

[figure not shown]

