**Table 6 Sensitivity of Sample Size to Standardized Effect Size for SSPs**

d	Target Power	Actual Power	N1 for RI	N2 for DI	Total N
0.6	0.8	0.81	34	68	102
0.6	0.85	0.86	39	78	117
0.6	0.9	0.9	45	90	135
0.63	0.8	0.81	31	62	93
0.63	0.85	0.85	35	70	105
0.63	0.9	0.9	41	82	123
0.66	0.8	0.8	28	56	84
0.66	0.85	0.85	32	64	96
0.66	0.9	0.9	37	74	111
0.69	0.8	0.81	26	52	78
0.69	0.85	0.85	29	58	87
0.69	0.9	0.9	34	68	102
0.72	0.8	0.81	24	48	72
0.72	0.85	0.85	27	54	81
0.72	0.9	0.91	32	64	96
0.75	0.8	0.81	22	44	66
0.75	0.85	0.86	25	50	75
0.75	0.9	0.9	29	58	87

**Figure 5 Relationship between Minimum Sample Size Required for RI Arm and the Assumed Standardized Effect Size for SSPs****Sample Size of PSPs:**

For PSPs, its sample size will be considered in a similar way to that of SSPs. With the cap 220 on the number of enrolled PSPs and the assumption on the dropout rate about 15% across arms, a series of targeted power will be investigated to determine the number of PSPs needed in each arm that will ensure the detection of the various differences between two arms (DI vs RI) in term of mean FIM score of PSPs at Month 13.

[figure not shown]
With the dropout rate 15%, at most 187 out of the capped 220 PSPs will remain in both DI arm and RI arm with the ratio 2:1 at Month 13, and the absolute value of standardized effect size d will range from 0.44 to 0.51 when the study power increases from 0.80 to 0.90 as shown in [Table 7](#), where [Figure 6](#) illustrates the relationship between d>0 and the study power.

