**Figure 7 Relationship between Minimum Sample Size Required for RI Arm and the Assumed Standardized Effect Size for PSPs**

### 5.3. Essential Analysis

The primary endpoint in terms of feasibility is SSPs' mean FIM score at Month 13 under Dynamic Implementation (DI) arm and Routine Implementation (RI) arm respectively, and the difference of their mean FIM scores between arms. For FIM of SSPs and the difference between arms, descriptive statistics including 95% confidence intervals will be displayed for these estimates. Mean FIM scores will be compared between the two implementation arms to test if the observed difference is statistically significant. In

addition, distribution of FIM items scores will also be compared. P-values will be reported for these comparisons.

To address the potential intra-cluster correlation effect due to the cluster randomization design, classical methods such as mixed effects linear regression model or Generalized Estimating Equations will be utilized. Besides the analysis on the subject level, the stratification analysis will be performed at the site level to evaluate the impact of the capacity of sites (high volume vs low volume) in responses to two implementation strategies imposed on SSPs. Exploratory analysis will be undertaken to assess the variability of responses by other factors such as subset of implementation strategies.

In addition to summary of mean FIM scores of SSPs at different timepoints, the change in mean FIM scores from baseline will be analyzed at the designated timepoints. For the specific Telehealth implementation strategy on SSPs, the subgroup analysis on FIM scores including change from baseline will be conducted.

The FIM scores of PSPs will be summarized in the same way as those of SSPs. In addition, subgroup analysis on PSPs will include, but not limited to, factors such as demographic, baseline characteristics, study arm, clinic characteristics and APRETUDE initiation method. To address the potential differential dropout rates of PSPs between arms, appropriate imputation methods will be undertaken to handle missing data of different type.

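### Section 5.1 tests both hypotheses with an ANOVA that has no site term, Section 5.3 names a cluster-adjusted model for the same comparison, and the protocol does not say which governs

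*Protocol*

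**What the plan says.** **Design.** Sites are the unit of randomisation. The abstract states "Randomization will occur at the level of study sites", and Section 4.1 gives about 12 clinics in DI and about 6 in RI.

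**Section 5.1.** The primary hypothesis concerns the mean FIM score of staff participants (SSPs) at Month 13. The secondary hypothesis concerns the mean FIM score of patient participants (PSPs). The test is fixed for both: "The two-way ANOVA will be used to test each of the above hypothesis with clinic volume as the stratification factor".

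**Section 5.3.** For the same SSP comparison, with p-values, this section says that to handle intra-cluster correlation "classical methods such as mixed effects linear regression model or Generalized Estimating Equations will be utilized". It then adds: "Besides the analysis on the subject level, the stratification analysis will be performed at the site level". PSP scores are to be summarised in the same manner as SSP scores.

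**Abstract, Analysis Methods.** "A hypothesis test will be conducted to determine if the observed difference is statistically significant" is followed directly by the same sentence on a mixed model or GEE.

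**Section 5.2.** Sizing is on individuals, 90 SSPs and 187 evaluable PSPs, and states that the ICC is left out.

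**The concern.** Sections 5.1 and 5.3 each say what will be done for one and the same comparison, and they describe different tests. A two-way ANOVA on arm and volume treats everyone within a volume stratum as independent unless the data are first reduced to site means. Staff at one site share a clinic, a workflow and the same implementation support, so some correlation is to be expected; the protocol itself anticipates it in Section 5.3.

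If Section 5.1 governs and is run on individuals, ordinary differences between sites can produce a significant DI versus RI result when the strategies do not differ. If Section 5.3 governs, Section 5.1 is wrong as written. Until this is settled, two p-values have protocol support for the primary hypothesis. The trial is open-label, and Section 5 plans interim looks at the primary objective, so the choice should not remain open.

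**Working it through.** **1. Inputs.** 18 sites, 12:6 (Section 4.1); about 9 high and 9 low volume (Section 3.1); 90 SSPs, so 90/18 = 5 per site; 187 evaluable PSPs, so 187/18 = 10.4, taken as 10 per site; SSP standard deviation 0.59 (Section 5.2). Assumed because the protocol does not give them: ICC from 0.01 to 0.20, equal site sizes, 6 DI and 3 RI sites in each volume stratum, and a two-sided alpha of 5% (consistent with the 95% intervals).

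**2. Reproducing the plan's sizing.** For a two-sample t-test with n = 30 and 60, the standard error in SD units is √(1/30 + 1/60) = 0.2236. The detectable d is 0.633, 0.677 and 0.733 at 80%, 85% and 90% power; Table 4 gives 0.63, 0.68 and 0.73. For 62 and 125 PSPs it is 0.437, 0.468 and 0.506; Table 7 gives 0.44, 0.47 and 0.51. The tables therefore correspond to an individual-level test with no clustering at a two-sided 5%, which is the same assumption as an ANOVA on individuals.

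**3. Type I error of the arm + volume ANOVA on individuals.** Design effect DE = 1 + (m − 1) × ICC. Approximate rejection rate under the null = 2 × [1 − Φ(1.96/√DE)]. For example, SSPs at ICC 0.10: DE = 1 + 4 × 0.10 = 1.40, 1.96/√1.40 = 1.656, rate 9.8%. Simulation used 40,000 null trials per ICC.

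| Assumed ICC | 0.01 | 0.02 | 0.05 | 0.10 | 0.20 |
|---|---|---|---|---|---|
| SSP, DE (m = 5) | 1.04 | 1.08 | 1.20 | 1.40 | 1.80 |
| SSP, formula | 5.5% | 5.9% | 7.4% | 9.8% | 14.4% |
| SSP, simulated | 5.4% | 5.8% | 7.5% | 9.6% | 14.6% |
| PSP, DE (m = 10) | 1.09 | 1.18 | 1.45 | 1.90 | 2.80 |
| PSP, formula | 6.0% | 7.1% | 10.4% | 15.5% | 24.1% |
| PSP, simulated | 6.2% | 7.2% | 10.6% | 15.7% | 25.0% |

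Adding an arm-by-volume interaction changes the simulated rates by at most 0.2 percentage points.

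**4. Valid alternatives in the same setting.** The ANOVA on the 18 site means (18 − 3 = 15 df) rejects 4.8% to 5.1% of the time throughout. A mixed model with a random site intercept, referred to t on 15 df and checked at ICC 0.01, 0.05, 0.10 and 0.20, rejects 3.0% to 5.0% for SSPs and 3.2% to 5.1% for PSPs, so it can be somewhat conservative.

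**5. Precision for SSPs.** The 95% half-width for the individual ANOVA is 0.44 SD × 0.59 = 0.26. For site means it averages 0.479, 0.488, 0.514, 0.554 and 0.629 SD at the five ICCs, which times 0.59 is 0.28, 0.29, 0.30, 0.33 and 0.37.

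**The case against.** The strongest defence is that the two sections fit together. Section 5.3 ties its stratification analysis by clinic volume to the site level, and the Section 5.1 ANOVA is the one stratified by clinic volume, so it might be meant for site means, where it is valid. Alternatively, a mixed model with arm, volume and a random site effect can be seen as an extension of a two-way ANOVA. The sponsor clearly knows about the clustering, and Section 5 calls itself a summary with technical detail to follow in the SAP. The inflation also needs two conditions, that Section 5.1 governs and that it is run on individuals. Even then it is 5.4% to 7.5% for the primary SSP test at ICC 0.01 to 0.05; the largest figures belong to the secondary PSP hypothesis.

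Part of this stands. The unit of analysis is unstated, so the site-mean reading cannot be excluded, and the choice of degrees of freedom or of a GEE standard error can be left to the SAP. For PSPs the conflict arises only by reference, since Section 5.3 speaks of summarising their scores in the same manner. But neither reconciling reading is written down, and the individual-level sizing favours the invalid one. Deferral to the SAP covers more detail on the analyses described; it does not choose between two different analyses that the protocol itself prescribes.

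**Conclusion.** The concern holds. For the primary SSP comparison the protocol prescribes two different tests, and one of them, on the reading that the sizing favours, does not hold its level. The excess is 0.4 to 9.6 percentage points over a nominal 5% for SSPs and 1.2 to 20.0 points for PSPs across ICC 0.01 to 0.20. It is modest for the primary hypothesis if the ICC is small, and zero if the ANOVA was meant for site means. The figures rest on the assumed ICC range, equal site sizes, the assumed split of arms within volume strata and a two-sided 5% level. The contradiction between the sections rests on none of these. Because it concerns the primary test, it must be corrected.

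**What to change.** Replace the last sentence of Section 5.1 with one cluster-respecting primary test for both hypotheses. A suitable choice is a linear mixed model with arm and clinic volume as fixed effects, a random site intercept and small-sample degrees of freedom, with the 95% confidence interval from the same model. An ANOVA on site means with arm and volume would serve as an alternative or as a sensitivity analysis. Delete the ANOVA without a site term, or state that its unit is the site mean. Align Section 5.3 and the abstract so that all three name the same test, before any interim or final database lock.

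The change is to wording only; no data collection or design feature alters. Its statistical cost is the wider interval shown above, from 0.26 to between 0.28 and 0.37 for SSPs.

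Power also falls below the stated 80%. With a cluster-adjusted test on 15 df (noncentrality d/SE/√DE; PSPs at 10.4 per site), it is:

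| Assumed ICC | 0 | 0.05 | 0.10 | 0.20 |
|---|---|---|---|---|
| SSP, d = 0.63 | 0.75 | 0.67 | 0.60 | 0.50 |
| PSP, d = 0.44 | 0.75 | 0.59 | 0.48 | 0.35 |

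That loss comes from having only 18 sites and from the clustering, neither of which the sizing allows for. The corrected test makes it visible, and the sponsor should expect it when Section 5.1 is revised.
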